6.3.8 Vital signs

Vital signs assessments will be performed at the times indicated in Table 1.

6.3.8.1 **Pulse and blood pressure**

Supine blood pressure and pulse rate will be measured using standard equipment with an appropriate cuff size after 10 minutes rest on a bed.

6.3.9 **Ophthalmology**

Baseline and postdose ophthalmology assessments will be performed at the time indicated in Table 1

The same ophthalmic expert will perform ophthalmic assessments on each occasion where possible. The ophthalmic assessment will be performed at baseline and again post-study.

The following assessments will be performed in the order stated:

- Visual acuity (best corrected) using both distance and near vision charts and Amsler grid text
- Schirmer's test without anaesthesia read after 5 minutes (this test should be done before instillation of stains or dilatory agents) pre-study examination only
- Slit lamp examination:
 - Evert lid and assess for presence of tarsal, fornicial, bulbar, and circumcorneal hyperaemia. Before staining, photograph any abnormalities to be captured
 - Apply 1 drop of 2% fluorescein followed by 1 drop of normal saline
 - Photograph any abnormalities
- Fundoscopy following pupil dilation and intraocular pressure measurement will be performed at pre-study examination only, but may be repeated at the ophthalmologist's discretion. Fundoscopy may be the last appropriate test.

During the study the subjects will be asked to report if they experience any eye symptoms such as dry eyes, grittiness, or irritation. In case of clinically relevant ophthalmological abnormalities, an additional full examination (as detailed above) will be performed.

Any corneal changes must be monitored frequently, with therapeutic intervention as appropriate until resolution. Any abnormalities elicited will be recorded as an AE.

6.4 **Pharmacokinetics**

6.4.1 Collection of samples

Blood samples (see Table 3) for determination of AZD8931 and o-desmethyl AZD8931 (if feasible) concentrations in plasma as well as total radioactivity in whole blood and plasma will be taken at the times presented in the study assessments (Table 1).

Blood samples (see Table 3) for metabolite profiling will be taken at the times presented in the study assessments (Table 1). The metabolite profiling and identification in plasma will be described in a separate report.

Urine and faeces samples for determination of total radioactivity in urine and faeces will be taken at the time intervals presented in the study assessments (Table 1). The metabolite profiling and identification in urine and faeces will be described in a separate report.

Blood, urine, and faeces samples will be collected, labelled, stored, and shipped as detailed in the Laboratory Manual. The date and time for collection of blood, urine, and faeces samples will be recorded in the Electronic Data Capture (EDC) System.

For blood volume see Section 7.1.

6.4.2 Determination of drug concentration

Samples for determination of AZD8931 and o-desmethyl AZD8931 concentrations in plasma will be analysed by . Samples for determination of radioactivity in blood, plasma, urine, and faeces will be analysed by a laboratory to be appointed on behalf of AstraZeneca.

Full details of the analytical method used will be detailed in a separate bioanalytical report.

6.5 **Pharmacogenetics**

6.5.1 Collection of pharmacogenetic samples

The blood sample for genetic research will be obtained from the subjects at screening (timing of sample collection at the discretion of the study centre). Although genotype is a stable parameter, early sample collection is preferred to avoid introducing bias through excluding subjects who may discontinue due to an AE, such subjects would be important to include in any genetic analysis. If for any reason the sample is not drawn at screening, it may be taken at any visit until the last study visit. Only 1 sample should be collected per subject for genetics during the study. Samples will be collected, labelled, stored, and shipped as detailed in the Laboratory Manual.

For blood volume see Section 7.1.

7. BIOLOGICAL SAMPLING PROCEDURES

7.1 Volume of blood

The total volume of blood that will be drawn from each subject in this study is presented in Table 3.

Assessment		Sample volume (mL)	No. of samples	Total volume (mL)
Safety	Clinical chemistry	5	5	25
	Haematology	2	5	10
	Serology	3.5	1	3.5
Pharmacokinetic determination of AZD8931 and o-desmethyl AZD8931 (if applicable) concentrations in plasma		3	17	51
Whole blood total radioactivity		2	17	34
Plasma total radioactivity		2	17	34
AZD8931 metabolite profiling		10	5	50

Table 3Volume of blood to be drawn from each subject

Assessment		Sample volume (mL)	No. of samples	Total volume (mL)
Safety	Clinical chemistry	5	5	25
	Haematology	2	5	10
	Serology	3.5	1	3.5
Pharmacogenetics		10	1	10
Total				217.5

Table 3Volume of blood to be drawn from each subject

Additional collections of blood may continue at 24-hour intervals until radioactivity counts are <3 times the background count on 2 consecutive samples. However, the maximum volume to be drawn from each subject will not exceed 500 mL, ie, the same volume as would be drawn during a regular blood donation.

7.2 Handling, storage and destruction of biological samples

The samples will be used up or disposed of after analyses or retained for further use as described here.

Biological samples for future research can be retained on behalf of AstraZeneca for a maximum of 25 years following the Last Subject's Last Visit in the study. The results from future analysis will not be reported in the Clinical Study Report but separately in a Scientific Report.

7.2.1 Pharmacokinetic and/or pharmacodynamic samples

Samples will be disposed of after the Clinical Study Report has been finalised, unless retained for future analyses, see below.

Additional analyses may be conducted on the biological samples to further investigate the presence and/or identity of drug metabolites and/or to further investigate reproducibility of incurred samples and/or to further investigate stability of incurred samples. Any results from exploratory analyses to identify drug metabolites will be reported elsewhere. Incurred sample reproducibility analysis, if any, will be performed alongside the bioanalysis of the test samples and reported in a separate bioanalytical report.

7.2.2 Pharmacogenetic samples

The processes adopted for the coding and storage of samples for genetic analysis are important to maintain subject confidentiality. Samples will be stored for a maximum of 25 years, from the date of the Last Subject's Last Visit, after which they will be destroyed. DNA is a finite resource that may be used up during analyses. Samples will be stored and used until no further analyses are possible or the maximum storage time has been reached.

For all samples irrespective of the type of coding used the DNA will be extracted from the blood sample. The DNA sample will be assigned a unique number replacing the information on the sample tube. Thereafter, the DNA sample will be identifiable by the unique DNA number only. The DNA number is used to identify the sample and corresponding data at the AstraZeneca genetics laboratories, or at the designated contract laboratory. No personal details identifying the individual will be available to any person (AstraZeneca employee or contract laboratory staff working with the DNA).

The samples and data for genetic analysis in this study will be single coded. The link between the subject enrolment code and the DNA number will be maintained and stored in a secure environment, with restricted access WITHIN the Clinical Genotyping Group Laboratory Information Management System (LIMS) at AstraZeneca. The link will be used to identify the relevant DNA samples for analysis, facilitate correlation of genotypic results with clinical data, allow regulatory audit, and to trace samples for destruction in the case of withdrawal of consent when the subject has requested disposal/destruction of collected samples not yet analysed.

7.3 Labelling and shipment of biohazard samples

The Principal Investigator will ensure that samples are labelled and shipped in accordance with the Laboratory Manual and the Biological Substance, Category B Regulations (materials containing or suspected to contain infectious substances that do not meet Category A criteria), see Appendix C "IATA 6.2 Guidance Document".

Any samples identified as Infectious Category A materials are not shipped and no further samples will be taken from the subject unless agreed with AstraZeneca and appropriate labelling, shipment and containment provisions are approved.

7.4 Chain of custody of biological samples

A full chain of custody is maintained for all samples throughout their lifecycle.

The Principal Investigator will keep full traceability of collected biological samples from the subjects while in storage at the study centre until shipment or disposal (where appropriate) and will keep documentation of receipt of arrival.

The sample receiver will keep full traceability of the samples while in storage and during use until used or disposed of or until further shipment and will keep documentation of receipt of arrival.

AstraZeneca will keep oversight of the entire life cycle through internal procedures, monitoring of the study centre, and auditing of external laboratory providers.

Samples retained for further use are registered in the AstraZeneca biobank system during the entire life cycle.

7.5 Withdrawal of informed consent for donated biological samples

If a subject withdraws consent to the use of donated biological samples, the samples will be disposed of/destroyed, and the action documented. If samples are already analysed, AstraZeneca is not obliged to destroy the results of this research.

As collection of the biological samples is an integral part of the study, then the subject is discontinued from further study participation.

The Principal Investigator will:

- Ensure subjects' withdrawal of informed consent to the use of donated samples is notified immediately to AstraZeneca
- Ensure that biological samples from that subject, if stored at the study centre, are immediately identified, disposed of/destroyed, and the action documented
- Ensure the laboratory(ies) holding the samples is/are informed about the withdrawn consent immediately and that samples are disposed/destroyed, the action documented and the signed document returned to the study centre
- Ensure that the subject and AstraZeneca are informed about the sample disposal

AstraZeneca will ensure the central laboratory(ies) holding the samples is/are informed about the withdrawn consent immediately and that samples are disposed of/destroyed and the action documented and returned to the study centre.

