2.3 Exploratory objectives

- 1. Collect optional blood samples for DNA extraction and storage to enable an investigation into the impact of polymorphisms on the absorption, distribution, metabolism, and excretion (ADME)-related genes, eg, the effect of cytochrome P450 (CYP) 2D6 genotype on AZD8931 PK (the data will be reported separately)
- 2. Perform possible exploratory analysis of significant metabolites in plasma, urine, and faecal samples (the data will be reported separately)

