6.2 Data collection and enrolment

Each subject will undergo screening in the 28 days before Visit 2. This will consist of:

- 1. Obtaining written informed consent before starting any study specific procedures
- 2. Recording of demographic data (date of birth, sex, race)
- 3. Height, weight, and calculation of BMI
- 4. A standard medical, medication, and surgical history with review of the inclusion and exclusion criteria with the subject
- 5. A complete physical examination
- 6. Habits of nicotine and alcohol use
- 7. Vital signs
- 8. Recording of a resting 12-lead paper ECG
- 9. A blood sample for routine clinical chemistry and haematology, and screen for hepatitis B surface antigen, antibodies to hepatitis C virus and antibodies for HIV
- 10. A urine sample for routine urinalysis and drugs of abuse screen (excluding alcohol)
- 11. Assessment of AEs
- 12. Assessment of any concomitant medication
- 13. Ophthalmology assessment
- 14. Blood sample for pharmacogenetics (optional)

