8.4 Informed consent

The Principal Investigator will:

- Ensure each subject is given full and adequate oral and written information about the nature, purpose, possible risk, and benefit of the study
- Ensure each subject is notified that they are free to discontinue from the study at any time

- Ensure that each subject is given the opportunity to ask questions and allowed time to consider the information provided
- Ensure each subject provides signed and dated informed consent before conducting any procedure specifically for the study
- Ensure the original, signed Informed Consent Form(s) is/are stored in the Investigator's Study File
- Ensure a copy of the signed Informed Consent Form is given to the subject
- Ensure that any incentives for subjects who participate in the study as well as any provisions for subjects harmed as a consequence of study participation are described in the Informed Consent Form that is approved by an EC

A separate Informed Consent Form will be provided for genotyping.

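### Section 7.5 discontinues any subject who withdraws sample consent and does not exempt the optional genetic sample; it should be reconciled with Sections 7.2.2 and 8.4

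*Protocol*

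**What the plan says.** Section 7.5 is triggered by withdrawal of consent to the use of donated samples, with no sample type named: "If a subject withdraws consent to the use of donated biological samples, the samples will be disposed of/destroyed, and the action documented". It then states the consequence for the subject: "As collection of the biological samples is an integral part of the study, then the subject is discontinued from further study participation". The section closes a chapter that covers both the pharmacokinetic samples (7.2.1) and the pharmacogenetic samples (7.2.2), and it exempts neither.

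Elsewhere the genetic sample is treated as a voluntary addition. The first exploratory objective in Section 2.3 is to "Collect optional blood samples for DNA extraction and storage". Table 1 and the screening list in Section 6.2 also mark it as optional. Section 8.4 adds: "A separate Informed Consent Form will be provided for genotyping". Section 6.5.1 prefers collection at screening, but otherwise "it may be taken at any visit until the last study visit".

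Section 7.2.2 has its own withdrawal wording. The link between the enrolment code and the DNA number is kept, among other reasons, so that samples can be traced for destruction "in the case of withdrawal of consent when the subject has requested disposal/destruction of collected samples not yet analysed". It does not mention whether the subject stays in the study.

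**The concern.** The rule rests on a premise that is true of the blood, urine and faeces needed for the primary objective and untrue of the DNA sample. A subject who declines the DNA sample at screening can take part in full. One who gives it and later revokes only that consent would, if Section 7.5 is followed to the letter, be discontinued.

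Timing makes this matter. The study gives a single dose on Day 1, so discontinuation after that spares no drug or radiation exposure. What it ends is the remaining mass-balance collection (primary objective) and the remaining scheduled safety assessments (secondary objective), for a reason connected with neither.

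A second ambiguity lies in the instructions to the investigator in Section 7.5. The one on samples held at the centre refers to the subject's samples generally, not to the type for which consent was withdrawn. Read literally, destruction could extend to stored pharmacokinetic and excreta samples.

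**Working it through.** The plan states no figure on this point. The check is a comparison of sections and a count from Table 1.

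**Scope of the rule**

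| Question | Mandatory PK, radioactivity and safety samples | Genetic sample |
|---|---|---|
| Needed for the primary or secondary objective? | Yes (2.1, 2.2) | No, exploratory only (2.3) |
| Can a participant decline it? | No | Yes (2.3, 6.2, Table 1) |
| Separate consent form? | None mentioned | Yes (8.4) |
| Withdrawal text | 7.5: destroy and discontinue | 7.5 as above; 7.2.2: destroy, silent on continuing |

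Sections 5.8 and 5.8.1 (withdrawal) and 8.4 (consent) do not narrow Section 7.5. Because Section 6.5.1 allows the sample at any visit, a genetic consent can be in force throughout the residential period.

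**What one literal application removes**

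Take discontinuation just after the 48-hour collections, as an illustration. From Table 1, notes j, l and m:

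- Faeces: 10 postdose intervals (0 to 24 hours, then every 24 hours to 240). Two are complete by 48 hours, so 10 − 2 = 8 are lost, 8/10 = 80%.
- Urine: 12 postdose intervals (0–6, 6–12, 12–24, 24–48, then eight of 24 hours). Four are complete, so 12 − 4 = 8 are lost, 8/12 = 67%.
- Blood: 16 postdose times (1, 2, 4, 6, 8, 12, 24, 48, then 72 to 240 hours every 24). Eight are taken, so 16 − 8 = 8 are lost, 8/16 = 50%.
- Safety: the Day 11 vital signs, ECG and laboratory tests, and all of Visit 3. Visit 3 holds the only scheduled postdose physical and eye examinations.

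**Share of the study**

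One subject is 1/6 = 16.7% of the planned sample. Falling from 6 to the evaluable minimum of 4 in Section 5.2 takes 6 − 4 = 2 such losses.

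**Effect on the recovery summary**

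Section 12.2 keeps a withdrawn subject's data up to discontinuation and takes no action for missing data. His cumulative recovery would then cover only the period before he left. If it falls d percentage points short of what 240 hours would have shown and enters the summary with the other five, the arithmetic mean of six drops by d/6. The protocol gives no excretion time course, so d cannot be estimated. The interval counts measure lost collections, not lost radioactivity.

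**The case against.** The strongest reply is that the sentence limits itself. It gives the integral nature of collection as its reason, and an optional sample is not integral, so an ordinary reader could confine the rule to the mandatory samples. Section 7.2.2, the more specific provision, speaks only of destroying DNA samples. The genotyping consent form, which is not available here, may also set out the terms of revocation. This reading is reasonable, and it means the protocol does not clearly order discontinuation in the genetic case. What survives is that neither section says so, and site staff would have to infer it while a dosed subject is in residence.

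The loss is also cushioned. A discontinued subject may be replaced (5.2, 5.8.1). Data up to discontinuation are used (12.2). He is asked about adverse events, seen by an investigator if possible, and followed for those events (5.8.1). Section 6.3.9 provides an extra full eye examination for relevant abnormalities during the study. Section 7.5 does not oblige the sponsor to destroy results already obtained. These points stand, with limits. Replacement is discretionary, aims only at 4 evaluable subjects, and would dose one more man in a study meant to expose as few as possible. The scheduled Visit 3 eye examination is not guaranteed after withdrawal.

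Two stronger readings are tempting. A reader might infer that retention of samples for future research has the same problem, since Section 7.2 says "Biological samples for future research can be retained on behalf of AstraZeneca for a maximum of 25 years". But no section makes retention optional or gives it a separate consent, so the contradiction is documented only for the DNA sample. A reader might also infer that subjects are pressed not to revoke genetic consent. What they are told is unknown without that consent form, so the protocol does not support this.

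**Conclusion.** The point holds as a wrongly scoped rule of low severity. Section 7.5 applies to all donated samples a consequence whose stated reason covers only the mandatory ones, and Section 7.2.2 leaves open whether a subject who revokes genetic consent stays in. Harm to the mass-balance data needs four things together: the subject gave the DNA sample, he revokes only that consent, he does so between dosing and 240 hours, and the site applies Section 7.5 literally. The documents give no frequency, and it is likely rare. When it does happen, up to one sixth of the planned subjects would have truncated collection, with an effect on recovery that cannot be quantified from the protocol. Destruction of his pharmacokinetic and excreta samples is a possible literal reading, not a stated intention.

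**What to change.** Reconcile Section 7.5 with Sections 7.2.2 and 8.4:

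- Limit discontinuation to withdrawal of consent for the mandatory study samples.
- State that withdrawal of the optional genetic consent leads only to destruction of the DNA sample, and that the subject continues all blood, urine and faeces collections and attends Visit 3.
- Limit the destruction instructions in Section 7.5 to the sample type for which consent was withdrawn.
- Add a cross-reference from Section 7.2.2, and check that the genotyping consent form agrees.

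The cost is one paragraph in the protocol and matching consent wording. No procedure, sample or subject is added.

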8. ETHICAL AND REGULATORY REQUIREMENTS

8.1 Ethical conduct of the study

The study will be performed in accordance with ethical principles that have their origin in the Declaration of Helsinki and are consistent with International Conference on Harmonisation/Good Clinical Practice, applicable regulatory requirements, and the AstraZeneca policy on Bioethics and Human Biological Samples.

8.2 Subject data protection

The Informed Consent Form will incorporate (or, in some cases, be accompanied by a separate document incorporating) wording that complies with relevant data protection and privacy legislation.

AstraZeneca will not provide individual genotype results to subjects, any insurance company, any employer, their family members, general physician, or any other third party, unless required to do so by law.

Extra precautions are taken to preserve confidentiality and prevent genetic data being linked to the identity of the subject. In exceptional circumstances, however, certain individuals might see both the genetic data and the personal identifiers of a subject. For example, in the case of a medical emergency, an AstraZeneca Physician or an Investigator might know a subject's identity and also have access to his genetic data. Also regulatory authorities may require access to the relevant files, though the subject's medical information and the genetic files would remain physically separate.

8.3 Ethics and regulatory review

An Ethics Committee (EC) should approve the final Clinical Study Protocol, including the final version of the Informed Consent Form and any other written information and/or materials to be provided to the subjects. The Investigator will ensure the distribution of these documents to the applicable EC, and to the study centre staff.

The opinion of the EC should be given in writing. The Investigator should submit the written approval to AstraZeneca before enrolment of any subject into the study.

The EC should approve all advertising used to recruit subjects for the study.

AstraZeneca should approve any modifications to the Informed Consent Form that are needed to meet local requirements.

If required by local regulations, the Clinical Study Protocol should be re-approved by the EC annually.

Before enrolment of any subject into the study, the final Clinical Study Protocol, including the final version of the Informed Consent Form, is approved by the national regulatory authority or a notification to the national regulatory authority is done, according to local regulations.

AstraZeneca will handle the distribution of any of these documents to the national regulatory authorities.

AstraZeneca will provide regulatory authorities, EC, and Principal Investigators with safety updates/reports according to local requirements, including suspected unexpected serious adverse reactions (SUSARs), where relevant.

